Regulatory changes and procedural changes will be managed by the PIs at the University of Miami and communicated with [name] at the University of Connecticut. Compliance with local regulatory policy will be the responsibility of the PIs at each site. To ensure that sites are

using the most up-to-date protocol documents and study materials, the PI's will have at least weekly meetings to discuss progress and any issues that may arise during the research. In addition, joint meetings will take place regularly with the project coordinator(s) as well as the IEs. The project coordinator(s) will be responsible for implementing procedural changes at the CMHCs. The PIs and the project coordinator(s) will communicate regularly with the IEs as well, to ensure fidelity to the project procedures and provide updates, should these procedures change.

Upon completion of the study, a final meeting will take place that the University of Miami. During this meeting, data analyses and manuscript preparation. All UM Study staff, [name] from UConn, and [name], the study's statistical consultant, will attend this meeting (their travel has been accounted for in the grant budget).

19) Community-Based Participatory Research*

N/A

20) Sharing of Results with Subjects*

The data collected from this study is primarily for research purposes. All assessments (including the ADIS-5 C/P) are research assessments used for the purposes of assessing study eligibility and outcomes. No information will be shared with legal guardians or participants over the age of 18 without a direct request. No information will be shared with others without a written release signed by the legal guardian or a participant over the age of 18. The consent form will inform participants that the study may share some of their assessment results with their clinician to help with treatment planning or to manage crises.

Information shared with parents/guardians and/or participants will be consistent with standard clinical practice at each of the sites (for example, therapists may wish to meet with guardians during the session to discuss the adolescent's progress and functioning). Any assessments or results derived for research purposes will be shared on an as-needed basis. For example, if ADIS-5 assessment results suggest possible suicidality that is not otherwise captured by the treating clinician, this information will be shared with the appropriate individuals consistent with local laws and IRB regulatory policy.

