Official Title: Community study of Outcome Monitoring for Emotional disorders in Teens (COMET)

Principal Investigator Name: [name]

Version Number: 37

Version Date: 07/13/21

NCT Number: NCT02567266

1) **Protocol Title**

Community study of Outcome Monitoring for Emotional disorders in Teens (COMET)

2) **IRB Review History***

This project will be concurrently reviewed by the University of Connecticut Institutional Review Board (IRB), [contact].

3) **Objectives***

Emotional disorders, encompassing a range of anxiety and depressive disorders, are the most prevalent and comorbid psychiatric disorders in adolescence (Costello, Mustillo, Erkanli, Keeler, & Angold, 2003). Evidence-based therapies (EBTs) exist for single disorders (e.g., depression) or small clusters of disorders (e.g., anxiety disorders) but such EBTs are rarely integrated in community mental health clinic (CMHC) settings (Weiss, Catron, & Harris, 2000) and effect sizes are modest (40-50% of youth are treatment non-responders; (Walkup et al., 2008). Thus, methods for improving outcomes for these youth, particularly in CMHCs, are needed.

Transdiagnostic treatment, such as the Unified Protocols for the Treatment of Emotional Disorders in adults (Barlow et al., 2010), adolescents (UP-A; (J. Ehrenreich et al., 2008) and children ([name] & Bilek, 2012), is a promising new approach that uses a small number of common strategies to treat these conditions.

Another novel approach to improving clinical outcomes for youth with emotional disorders in CMHCs is the incorporation of a standardized measurement and feedback system (MFS). Emerging data suggests that MFS alone improves outcomes relative to treatment as usual (TAU) (Bickman, [name], Breda, De Andrade, & Riemer, 2011) but this has not been adequately tested in youth. Thus, our first aim is to examine the effectiveness of UP-A and a MFS (Youth Outcomes Questionnaires [YOQ; (Burlingame et al., 2005) relative to TAU, when delivered in CMHCs.

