A serious shortcoming of RCTs comparing EBTs to TAU is the confounding effects of increased measurement and feedback to clinicians as RCTs of EBTs often “build in” monitoring that is not part of standard care. This raises the possibility that increased monitoring, rather than the unique treatment components of the EBT, may be responsible for better outcomes over TAU. Thus, the second aim of this proposal is to isolate these effects from UP-A. Finally, this study will examine theoretically-linked mechanisms (both patient and provider level) of treatment outcomes of both the UP-A and the YOQ.

This project is an NIMH-funded collaborative R01 two-site trial (University of Miami (UM) grant PIs [name] and [name]; University of Connecticut PI [name] - for IRB purposes, the UM PI will be [name]). To address the three study aims, adolescents with anxiety and/or depressive disorders will be recruited from CMHCs in Miami and in CT (under the supervision of [name] at the University of Connecticut). Both adolescents and clinicians will be randomized to one of three conditions: (1) TAU alone; (2) TAU plus YOQ (TAU+); and (3) UP-A plus YOQ (UP-A). Research assessments by Independent Evaluators (IEs), children, parents, and clinicians will occur at baseline, 8 weeks and 16 weeks after treatment initiation and a 3-month follow-up.

The primary aims of this study are as follows:

- **Aim 1:** To examine the effectiveness of UP-A and YOQ compared to TAU. Aim 1 will test whether adolescents treated with UP-A and YOQ (plus TAU referred to as TAU+) demonstrate better response than those receiving TAU alone.
 - **Hypothesis 1:** A higher percent of adolescents treated with UP-A and TAU+, compared to TAU, will be treatment responders at 16 weeks after treatment initiation and at follow-up.
- **Aim 2:** To isolate the effects of evidenced-based measurement and feedback. Aim 2 will examine the relative effectiveness of the UP-A condition to the TAU+ condition.
 - **Hypothesis 2:** A higher percent of UP-A participants will be treatment responders than TAU+ participants at the 16 week and follow up assessments.
- **Aim 3:** To examine mechanisms theoretically associated with UP-A and YOQ.

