- (5) Adolescents with a reported history of intellectual disability or for whom there is substantial evidence (e.g., multiple learning disorders, extensive school-based accommodations for learning) that the cognitive level of the UP-A would make it inappropriate as an individual therapy modality, as determined via Family Background Questionnaire and/or based on PI judgement, will be excluded.

- (6) Given additional complexities obtaining informed consent, adolescents who are currently placed in the foster care system will be excluded.
- (7) If an agency is not able to provide at least three Spanish speaking therapists for the study, Spanish speaking adolescents and caregivers will be excluded at that agency because they could not be randomized to condition.

Clinician Inclusion Criteria:

- (1) Clinicians will be at least part-time employees or completing an approved internship of at least one year in duration at the study clinics.
- (2) Clinicians may conduct sessions in English or Spanish, but must be able to speak, read and understand English well enough to participate in English-language training and consultation meetings.

6) Number of Subjects*

The study aims to enroll approximately 222 adolescents aged 12-18 years (111 per site, at Miami and UConn) who meet study criteria. We anticipate that up to 300 participants (150 per site) will need to be recruited and screened to reach this goal.

At least eighteen clinician employees of the participating clinics (at least 9 at the Miami site and at least 9 at the UConn site) will be enrolled initially. Although every effort will be made to retain clinicians recruited to the investigation, it is anticipated that new clinicians will be trained annually to replace any clinician who leaves the organization or terminates study participation. Up to 80 (40 at each site) clinicians will participate in the project.

7) Study-Wide Recruitment Methods*

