Subject participation: Given the flexibility of the UP-A and TAU interventions, the exact duration of subject participation is estimated to be approximately 25 weeks, plus an additional 3 month follow-up. The UP-A is delivered in 8 to 21 weekly sessions, and no treatment duration is specified for the TAU conditions. 25 weeks is estimated to account for any additional time required for screening and intake (though, as noted above, all efforts will be made to ensure that treatment initiation is not delayed as a result of study participation). However, this interval may vary slightly due to holidays, typical clinic closures or other naturally occurring delays.

Assessments will take place at the CMHC, university setting, Center for Autism and Related Disorders office, and/or in another private setting within the community at baseline, approximately 8 weeks after treatment initiation (estimated to be mid-treatment), and approximately 16 weeks after treatment initiation ([post treatment] estimated to correspond with the length of UP-A treatment, based on average number of sessions from a recent RCT of the UP-A). Finally, a 3 month follow-up assessment will take place 7 months after treatment initiation (16 weeks + 3 months). All efforts will be made to have these assessments take place within a window of +/- 2 weeks when they are scheduled to occur.

Clinician participation: Though efforts will be made to retain the same clinicians throughout the study, we anticipate that there will be personnel turnover at the clinic sites. However, the maximum duration of clinician participation will be approximately four years, as this is the estimated timeline for study completion. UP-A clinicians who stopped participating in the larger study will still be invited to take part in the qualitative interview portion of the study.

Recruitment Timeline: We anticipate that recruitment of all subjects across both sites will take approximately 3.5 years.

Investigator Timeline: We estimate that the primary analyses will be completed at the end of the fourth year of the study once all study assessments have been completed.

Table 1: Study Timeline	Year 1 Months:				Year 2 Months:				Year 3 Months:				Year 4 Months:			
	1-3	4-6	7-9	10-12	1-3	4-6	7-9	10-12	1-3	4-6	7-9	10-12	1-3	4-6	7-9	10-12
Participant Recruitment and Assessment																
Enrolling clinicians	X Ongoing as needed															
Enrolling new adolescent/caregiver participants		X	X	X	X	X	X	X	X	X	X	X	X	X		

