Study assessments		X	X	X	X	X	X	X	X	X	X	X	X	X	X	X
Data Management Activities																
Final Database Ready																M-11
Final Session Recording Collected															M-7	
IE Coding of Tapes for Fidelity & Differentiation	Ongoing for consultation purposes														X	X
Data Analysis																X
Preparation of manuscripts																X

9) **Study Endpoints***

The primary study outcome will be treatment response. Response will be defined as a Clinical Global Impression-Improvement (CGI-I) of 1 or 2 at 16 weeks after treatment initiation and at the 3 month follow-up. Secondary outcomes will include scores on the Children's Global Assessment Scale (CGAS), Screen for Child Anxiety Related Emotional Disorders-Youth and

Parent Reports (SCARED/-P), and the Mood and Feelings Questionnaire-Self & Parent Reports (MFQ), as well as diagnostic status on Anxiety Disorders Interview Schedule for the DSM-5, Child Version, Child and Parent Report Forms (ADIS-5-C/P).

The following measures will be taken to monitor data relating to safety:

Throughout the study, trained study staff will monitor participants' risk of harm. It is possible that participants' clinical data might indicate, for example, that a parent or adolescent is at risk (e.g., adolescent or parent reports suicidal ideation, or an adolescent's physical safety or well-being is in question). In order to address such situations, all study therapists and staff will be thoroughly trained in the ethics of conducting research with human participants, and will be thoroughly educated about the project's data safety and monitoring procedures. All such incidents will be reported immediately to the principal investigators, and, if necessary, to the local IRB according to their policies.

In addition, we will use the short version of the Columbia-Suicide Severity Rating Scale (C-SSRS) at baseline, 16 weeks, and 3 month follow-up and following any evidence of suicidal ideation or significant adolescent deterioration. The C-SSRS allows the IE to gather information on suicidal behavior, suicide attempts, and presence and intensity of suicidal ideation. The information will be used to identify adolescents possessive of active suicidal ideation, intent or plan that may need to be excluded due to needs for more acute care.

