All project staff will be educated about the importance of confidentiality, and trained on procedures used to protect this within the study. Information about participants will be kept strictly confidential (to the extent permitted by law) and information about participants will not be released without a signed release form by the child's caretaker.

Data Analysis Plan:

We plan to use GLMM (multilevel modeling, MLM, with a logistic linking function) to examine treatment effects on the dichotomous primary outcome ("response", defined as CGI-I of 1 or 2). Additional clinician-rated (e.g., CGI-S, CSR) and questionnaire-based (e.g., SCARED, MFQ) outcomes are all continuous measures and will be analyzed using traditional MLM.

13) Provisions to Monitor the Data to Ensure the Safety of Subjects*

The Principal Investigators, in accordance with the policies outlined by the University of Miami and UConn Institutional Review Boards (IRBs), are responsible for ensuring the safety of participants and the integrity of research procedures. Throughout the study, the PIs will work with all staff, Co-I's, and grant consultants, to ensure compliance with the study's procedures and data and safety monitoring plan. Finally, a Data Safety Monitoring and Board has been appointed to monitor progress of the study and at least annually (more frequently if needed). The Board members are [name] and [name] from the University of Miami and [name] from UConn.

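### Must the plan be changed because it names no primary visit, test order or multiplicity rule for treatment response?

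*Combined protocol and SAP*

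**What the plan says.** Section 9 makes treatment response the primary outcome and defines it as "CGI-I) of 1 or 2 at 16 weeks after treatment initiation and at the 3 month follow-up". It does not rank the two visits.

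Section 3 gives two directional hypotheses on response. Hypothesis 1 is that a higher percentage of "adolescents treated with UP-A and TAU+, compared to TAU, will be treatment responders at 16 weeks after treatment initiation and at follow-up". Hypothesis 2 reads: "A higher percent of UP-A participants will be treatment responders than TAU+ participants at the 16 week and follow up assessments".

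The Data Analysis Plan in Section 12 consists of two sentences. The first announces a "GLMM (multilevel modeling, MLM, with a logistic linking function) to examine treatment effects on the dichotomous primary outcome", with response defined as CGI-I of 1 or 2 and no visit attached. The second covers the continuous outcomes. Neither they nor any other section gives an alpha, sidedness, test order or multiplicity rule.

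Three other places bear on the reading. The assessment schedule in Section 10 has the CGI-I rated separately at 16 weeks and at follow-up. Section 8 places the post-treatment assessment at "approximately 16 weeks after treatment initiation ([post treatment] estimated to correspond with the length of UP-A treatment". It also says that the "primary analyses will be completed at the end of the fourth year of the study once all study assessments have been completed".

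**The concern.** Section 9's *and* can be read in two ways: one endpoint (a responder must have CGI-I 1–2 at both visits) or response assessed at each visit. Hypothesis 1 can also be read as pooling UP-A and TAU+ against TAU, or as comparing each with TAU. Together these give 2 or 3 tests on a single endpoint, or 4 or 6 tests over two visits.

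Since the primary analyses wait for all assessments, both visits' results will be in hand when the choice is made. If any significant result could be called the primary finding, the chance of a false claim would be well above 5%, and a reader could not tell which result confirms which hypothesis. The two endpoint readings also give different response rates.

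**Working it through.** **The plan's own figure.** "The study aims to enroll approximately 222 adolescents aged 12-18 years" (Section 6). With 1:1:1 allocation (Section 10), 222 / 3 = 74 per arm. No response rates, power, alpha or intraclass correlation accompany it, so 222 cannot be re-derived.

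**Which reading do the passages support?**
- Both hypotheses speak of being a responder at named assessments.
- Section 12 defines response from a single CGI-I rating, with no both-visits condition.
- The CGI-I is scheduled separately at each visit.

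These lean towards response at each visit. Nothing strictly excludes a both-visits endpoint, or a model that fits the visits jointly with one effect per contrast.

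**How far apart are the two endpoints?** With response probability p at each visit and between-visit correlation φ, the both-visits rate is p² + φp(1 − p).
- p = 0.4, φ = 0.4: 0.16 + 0.4 × 0.24 = 0.256
- p = 0.6, φ = 0.8: 0.36 + 0.8 × 0.24 = 0.552

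So assumed visit rates of 40–60% become about 26–55%. The rates and correlations are assumptions.

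**Familywise error.** Inputs, all assumed because the plan gives none: three equal arms, two visits, normal test statistics, two-sided 5% per test, no clustering, between-visit correlation ρ from 0.4 to 0.9, and no true difference at either visit. Arm means are drawn as a at 16 weeks and ρa + √(1 − ρ²)·e at follow-up. A pairwise contrast is a difference divided by √2. The pooled contrast is (mean of UP-A and TAU+ minus TAU) divided by √1.5. There were 1,000,000 draws; ranges run from the lower to the higher value as ρ varies.

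| Success rule | Pooled H1 + H2 | Three pairwise contrasts |
|---|---|---|
| One endpoint, any direction | 9.7% | 12.2% |
| One endpoint, hypothesised direction | 4.9% | 6.6% |
| Either visit, any direction | 13.5–17.8% | 16.7–21.9% |
| Either visit, hypothesised direction | 6.9–9.1% | 9.1–12.0% |
| Same contrast at both visits, any direction | 1.4–5.8% | 1.9–7.6% |
| Same contrast at both visits, hypothesised direction | 0.7–2.9% | 1.0–4.0% |

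The last row is closest to the hypotheses, which are directional and join the visits with *and*. It assumes no effect at either visit. If effects were large at one visit and absent at the other, a false both-visits claim would be limited by the remaining visit, so its rate would approach the one-endpoint directional row: 4.9% or 6.6%.

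**Cost of imposing an order.** Two orders would hold familywise error at 5% on one visit: (a) UP-A versus TAU first, then the other two contrasts at 5% each; (b) a joint two-degree-of-freedom test of the three arms first, then all three contrasts at 5% each. Power was taken from 400,000 binomial draws with 74 per arm, without clustering or dropout.

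| Response TAU/TAU+/UP-A | Contrast | Ungated | (a) | (b) |
|---|---|---|---|---|
| 40/40/60% | UP-A v TAU+ | 71% | 57% | 64% |
| 40/40/60% | UP-A v TAU | 71% | 71% | 64% |
| 35/45/60% | UP-A v TAU+ | 47% | 46% | 46% |
| 35/45/60% | UP-A v TAU | 88% | 88% | 79% |

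Clustering by clinician and dropout would lower all of these.

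**The case for a change.** The strongest argument for a change is that the rule is unwritten. Two careful analysts could publish different primary results from this text, and nothing in the document stops the choice from following the data. The each-visit reading does not remove this: it leaves four or six tests and no statement on whether success at one visit is enough. Recording the choice before outcomes by arm are examined would need no new data.

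Much of that stands. The visit rule, the alpha and the pooled-or-separate question under Hypothesis 1 are not written down, and stating them would make the results easier to read. Two parts do not stand. First, the contrasts are not missing: Hypotheses 1 and 2 name them. Second, inflation of 14–22% is not a consequence of the plan. It requires an any-visit, any-direction success rule that appears nowhere and sits badly with hypotheses that state a direction and cite both visits.

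A specific remedy would also be a matter of preference. Making 16 weeks the sole primary visit would demote a follow-up to which the hypotheses give equal standing, in a protocol already at version 37 ("Version Date: 07/13/21"). Whether separately stated aims need joint familywise control is debated, and gating would make Aim 2 depend on the outcome of another comparison.

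**Conclusion.** This is missing detail that analysts can fill sensibly from the plan: fit the logistic mixed model, estimate the comparisons that Hypotheses 1 and 2 name, report both visits, and claim a hypothesis only where its direction is met at both. On that rule, familywise error is 0.7–2.9% (pooled Hypothesis 1) or 1.0–4.0% (three pairwise contrasts) with no effect at either visit, and approaches 4.9% or 6.6% at worst if effects are confined to one visit. The plan as written is therefore not shown to lead to a wrong result.

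A formal hierarchy is a trade-off. It would give strict 5% control and one headline result, but demote follow-up and, in the 40/40/60% example, cost 7 to 14 percentage points of power for UP-A versus TAU+ (71% to 64% or 57%).

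The conclusion rests on reading *and* as covering both visits, on assumed two-sided 5% tests, and on assumed correlations and response rates. It would weaken if a single significant result at one visit were presented as confirming a hypothesis; the 7–22% range would then apply. No change to the plan follows.

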This will be determined via baseline administration of the anticipated research version of the Anxiety Disorders Interview Schedule for the DSM-5, Child Version, Child and Parent Report Forms (ADIS-5-C/P), administered by an independent evaluator on study staff.
- (2) The adolescent is determined by the CMHC to be eligible for once weekly outpatient psychosocial services at the clinic and determined by the study IE to be appropriate for outpatient psychosocial intervention (e.g., no major cognitive impairment or active suicidality) based on clinical interview.
- (3) The adolescent lives (for at least 50% time) with legal guardian and this guardian is willing to attend treatment sessions and participate in study assessments (every effort will be made to encourage the same caregiver to participate in all assessments).
- (4) Adolescent and parent/guardian are able to complete all study procedures in English or Spanish.

Youth Exclusion Criteria:

- (1) Adolescents will be excluded if they are receiving concurrent psychotherapy, family therapy or similar psychosocial interventions.
- (2) Adolescents who are currently suicidal or who have engaged in suicidal behaviors within the past 6 months will be excluded (or discussed on a case by case basis). Specifically, the evaluator will meet with the IE supervisor and discuss the youth and parent responses obtained during the clinical evaluation and determine whether the youth is currently at risk of imminent suicidality and in need of an alternative treatment. The short version of the Columbia-Suicide Severity Rating Scale (C-SSRS) will be used to screen for suicidality at baseline. The C-SSRS allows the IE to gather information on suicidal behavior, suicide attempts, and presence and intensity of suicidal ideation. The information will be used to identify adolescents possessive or active suicidal ideation, intent or plan.
- (3) Adolescents with a substance abuse problem within the last 6 months, as assessed by the CRAFFT and ADIS-5-C/P, will be excluded.
- (4) Consistent with prior trials of the UP-A, youth with primary conditions not specified for exclusion (e.g., eating disorders, schizophrenia) will be screened. As long as study staff concur that an emotional disorder treatment focus is appropriate, these youth will be included.

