community. This assessment will include completion of some or all of the questionnaires/procedures listed in the “Pre Treatment” column in Table 2 and described in additional detail below. Randomization will take place following this first assessment once subjects have been deemed eligible for participation. If a participant is unable to begin treatment within 4 weeks of their initial baseline assessment, an abbreviated baseline re-assessment may be conducted prior to the start of treatment. This re-assessment will include review of the symptoms previously endorsed on the ADIS-5-C/P, SCARED, MFQ, YOQ, SDQ, DTS, and Avoidance Hierarchy (see Measures, below).

If any study assessment is to occur at the University of Miami, parents/guardians will be emailed a “paybyphone” link to register their car for parking through the University’s Parking and Transportation department. They may be asked to supply their license plate number so that study staff may register their car for them in the case of user or system error. License plate numbers will be discarded following termination of study participation, and will not be used for research purposes.

At every therapy session, some or all of the assessments/questionnaires listed in the “Every Session” column in Table 2 will be completed. Additional assessments will take place approximately 8 (mid-treatment) and 16 weeks (post-treatment) after treatment initiation, as well as 3 months after the post-treatment assessment. All efforts will be made to have these assessments take place within a specified time window in relation to the 8, 16, or 28 week time-point date. The windows allow for data collection up to two weeks before the time-point date and up to 2 weeks, 4 weeks, or 8 weeks after the time-point date for the mid-treatment, post-treatment, and follow-up evaluations respectively, although data may still be collected should participants miss this window. During these visits, some or all of the measures detailed in the respective assessment point columns in Table 2 will be administered. With the exception of the computer-based tasks (e.g., the BIRD task), all adolescent- and parent-report measures will be available in English and in Spanish. The Spanish translations of these measures will be submitted in an amendment prior to initiating data collection.

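### The optional re-assessment for adolescents who cannot start treatment within 4 weeks does not list the C-SSRS, the only measure described as asking about suicidal behaviour

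*Combined protocol and SAP*

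**What the plan says.** Section 5, Youth Exclusion Criterion 2, covers two things: adolescents who are suicidal now, and those "who have engaged in suicidal behaviors within the past 6 months will be excluded (or discussed on a case by case basis". It names the screening tool: "The short version of the Columbia-Suicide Severity Rating Scale (C-SSRS) will be used to screen for suicidality at baseline".

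Section 9 gives the timing of the C-SSRS: "at baseline, 16 weeks, and 3 month follow-up and following any evidence of suicidal ideation or significant adolescent deterioration". Table 2 has the same three scheduled points. Section 9 says the information serves to identify "adolescents possessive of active suicidal ideation, intent or plan that may need to be excluded due to needs for more acute care".

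Section 10 (Study Procedures) places randomization after the baseline visit: "Randomization will take place following this first assessment once subjects have been deemed eligible for participation". If treatment cannot begin within 4 weeks of baseline, "an abbreviated baseline re-assessment may be conducted prior to the start of treatment". Its content is then listed: "This re-assessment will include review of the symptoms previously endorsed on the ADIS-5-C/P, SCARED, MFQ, YOQ, SDQ, DTS, and Avoidance Hierarchy".

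The measure descriptions in section 10 state that the C-SSRS has parent and child versions. They also describe a form for later time points that covers ideation and behaviour over the interval from the previous assessment.

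**The concern.** The re-assessment exists because baseline information can go out of date when treatment is delayed. The list renews symptom scales, distress tolerance and avoidance, but not the instrument chosen to screen for suicidality. Suicidal behaviour is named in the exclusion criteria separately from current suicidality, so the plan itself treats the two as different things to ask about.

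What is at stake is clinical. An adolescent may make an attempt during the wait, report no current ideation at the re-assessment and show no evident deterioration. On the measures as described, that person could start treatment without being asked about the attempt, although section 9 intends C-SSRS information to identify those who may need more acute care. Sample size, power and the primary analysis are not affected.

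**Working it through.** No figure in the plan needs reproducing. The check sets the passages side by side, with one small piece of arithmetic on timing.

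**Step 1: what is listed.** The measures named for the re-assessment are the ADIS-5-C/P, SCARED, MFQ, YOQ, SDQ, DTS and Avoidance Hierarchy. That is seven, and the C-SSRS is not among them.

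**Step 2: what each is described as covering on suicide risk.**

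| Measure | Description in the documents | Suicidal behaviour mentioned? |
|---|---|---|
| C-SSRS (not listed) | Ideation, behaviour and attempts (sections 5, 9, 10) | Yes |
| ADIS-5-C/P | Present ideation or associated plans, asked of adolescent and parent (section 10) | No |
| YOQ | Suicidality is an example of a critical item (section 10, TAU+) | Not specified |
| MFQ | Number of items and a total score (section 10) | No |
| SCARED, SDQ, DTS, Avoidance Hierarchy | Anxiety, general psychopathology, distress tolerance, avoidance | No |

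Two details limit the cover from the ADIS and YOQ. The list is worded as a review of symptoms endorsed before. That wording may apply only to the ADIS, but where it applies it may not reach something new. Flagging of YOQ critical items is described for the YOQ online system, whereas at research assessments the YOQ is given in REDCap. The documents do not say whether the same flags are raised there.

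**Step 3: whether the trigger fills the gap.** Section 9 calls for a further C-SSRS after evidence of ideation or significant deterioration. Sections 9 and 13 also require action when clinical or questionnaire data show a decline, and immediate reporting of self-harm risk. All of these depend on something having come to light. An attempt that leaves no reported ideation and no visible decline need not set any of them off.

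**Step 4: timing.** Let W be the wait in weeks from baseline to treatment start. The next scheduled C-SSRS is nominally 16 weeks after treatment start, so the nominal interval between scheduled C-SSRS interviews is W + 16. The 16 weeks are common to every participant and do not change if the instrument is added. The part that belongs to this point is W alone: for these adolescents W > 4, so at treatment start the last scheduled C-SSRS is more than 4 weeks old. With the C-SSRS added, it would date from the re-assessment for those who have one.

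**Step 5: how many.** The documents give no count or proportion with W > 4. Section 10 (Randomization) anticipates slots within two weeks of baseline, which suggests that such waits should be uncommon. No estimate is made.

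**The case against.** The strongest reply has four parts.

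- **Suicide risk is not ignored at this contact.** The ADIS and YOQ are both listed and both touch on it, and any sign of ideation brings in the C-SSRS. This stands. A reader might infer that risk goes unasked during the wait, and the documents do not support that.
- **The item content of the ADIS, YOQ and MFQ is not in the documents.** One of them may contain a question about attempts. This also stands. A reader might infer that new suicidal behaviour is definitely not asked about; the text supports only that no listed measure is described as asking. The list is also introduced in a way that does not rule out further measures.
- **The re-assessment is not an eligibility re-screen.** Eligibility is settled before randomization, the list consists mainly of outcome and mediator measures, and it omits the CRAFFT as well. The exclusion also allows case-by-case discussion. So it would be wrong to say that the omission breaches an entry criterion or admits ineligible adolescents. The clinical reason remains, because section 9 uses the C-SSRS after entry too.
- **The assessment windows do not measure the problem.** Section 10 allows visits "up to two weeks before the time-point date and up to 2 weeks, 4 weeks, or 8 weeks after the time-point date" for the three later assessments. One might read from this a gap of 14 to 20 weeks after treatment start (16 − 2 to 16 + 4). That interval applies to every participant, including those who start promptly, and section 8 gives a narrower window of 2 weeks either side. Nor does the TAU arm, which has no session-by-session YOQ (222/3 = 74 planned), count those who wait. Neither figure sizes the affected group.

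These replies limit the point to a narrow gap. They do not remove it, since no measure on the list is described as asking about behaviour since baseline.

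**Conclusion.** The point holds in a narrow form. For adolescents whose treatment start is delayed beyond 4 weeks, the optional re-assessment does not list the one instrument described as asking about suicidal behaviour, and the remaining cover is partial. It is a safety-screening improvement to consider. The size cannot be given: the number affected is not stated and is expected to be small, and the added interval is the wait itself, which exceeds 4 weeks by definition.

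The conclusion rests on the documents' descriptions of the measures, and it assumes that the ADIS, YOQ and MFQ contain no direct question on recent attempts. If one of them does, and it is asked afresh at the re-assessment and acted on, the gap is smaller or absent. A reader might take the omission as a failure of the safety plan or a threat to the trial's results. The documents support neither reading.

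**What to change.** In section 10 (Study Procedures), add the C-SSRS to the re-assessment list, using the existing version for later time points with both adolescent and parent, so that it is given whenever the re-assessment is held. Add a matching note to Table 2. Handle positive answers through procedures already in the protocol: discussion between evaluator and supervisor (section 5), immediate report to the principal investigators (sections 9 and 13) and a safety plan (section 13).

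The cost is one entry in a list and some extra evaluator time with adolescent and parent. The documents do not say how much time. The contact is already planned and carries a $20 payment (section 23), so no new visit, instrument or staff is needed.

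The re-assessment remains optional, so the change does not reach adolescents for whom it is not held.
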